fMRI Validated LIFUP stimulation. We will use a Brainsonix ultrasound system with a transducer that fits in the 20-channel head coil. Participants will have the low-intensity focused ultrasound pulsation (LIFUP) transducer approximately aimed at the internal globus pallidus (GPI) using skin surface fiducials and gently strapped in place to their head. To minimize the ultrasound energy's exposure to air, a gel pad will be placed between the transducer and the participant's scalp. Participants will then be placed into the scanner where head scout scans will be used to guide more precise targeting adjustments. Once targeting is complete, a T1 image will verify the position of the LIFUP transducer and allow for estimation of the spatial location of the sonication beam focus (approximately 5mm long x 7mm diameter). Participants will receive active sonication at one visit and sham sonication at the other, the order of which will be randomized and counterbalanced across participants. The sonication protocol will consist of 20 ultrasound sonifications in a 30 s ON, 30 s OFF fashion at 650KHz, $Ispta \leq 720 \text{ mW/cm}^2$, 5% duty cycle, 0.5ms pulse width, 73.15mvP-P amplitude, and 100Hz pulse repetition frequency. For sham sonication, the gel pad will block close to all of the ultrasound energy from the transducer. For active sonication, the gel pad will allow the ultrasound energy to pass through. These gel pads are identical in appearance. Resting state fMRI (rs-fMRI) will be collected simultaneously with LIFUP (or sham) sonication.

MRI Data Acquisition: We will use a 3-Tesla Siemens PRISMA scanner. We will collect high-resolution 0.8 mm^3 T1-weighted images, pseudo-continuous arterial spin labeling (PCASL) images, and rs-fMRI images. Total time in the scanner will be approximately 75 minutes each session.

Analysis and Publications. MRI data analysis will begin immediately during data collection, as structural and functional MRI are used to ensure successful targeting of LIFUP sonication. Group level analysis will occur after data from 30 subjects have been collected.

This project has four main aims:

#1: Validate basal ganglia-thalamocortical (BGTC) network perfusion and resting state functional connectivity (rs-FC) is associated with Parkinson's Disease (PD) deficits in cognition and motor impairments.

#2: Use LIFUP to modulate neural activity in the GPI, and PCASL pre- and post- LIFUP to assess up-regulation of BGTC network perfusion.

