#3: Measure BGTC network rs-FC before, during, and after LIFUP stimulation.

#4: Assess potential LIFUP-related changes in motor function and their association with changes in perfusion and rs-FC.

PROCEDURES

MRI Analysis. Preprocessing and analyses will be performed using FSL Version 6.0 (www.fmrib.ox.ac.uk/fsl). Structural data will be linearly registered to the standard MNI152 T1 2mm brain. Processing of fMRI data will include correcting for motion artifacts (using framewise displacement, DVARS, within-subject independent component analysis, and outlier removal),

slice timing correction, high-pass temporal filtering ($t > 0.01$ Hz) unwarping, and spatial smoothing (Gaussian Kernel FWHM = 8mm). Functional data will be linearly registered to stereotaxic MNI space and co-registered with anatomic data for each participant. Subjects with greater than 0.5mm mean framewise displacement will be excluded from analyses. PCASL scans will be transferred to MNI space using non-linear registration in FSL and then linearly registered with anatomic data for each participant.

Stimulation-related fMRI. rs-fMRI will be collected continuously during the LIFUP stimulation paradigms. A block-design model will be used to statistically compare the blood oxygenation level dependent (BOLD) signal during LIFUP stimulation blocks to the BOLD signal during no-stimulation blocks. To examine LIFUP-related network connectivity, we will use a seed-based approach and examine whole brain connectivity with the LIFUP target of interest⁶⁹ and compare between stimulation (on-off) conditions using psychophysiological interaction modeling (PPI)⁷⁰. We will also use dynamic connectivity to evaluate changes in connectivity across the course of the LIFUP stimulation paradigm.

RS-fMRI. We will compare rs-FC before and after stimulation. Independent component analyses (ICA) will be used to statistically extract functional networks from each participant's rs-fMRI. Dual-regression analysis will then compare resting state networks between baseline and post-LIFUP to determine the effect of LIFUP on resting state functional connectivity. Age, sex and education will be included as additional regressors.

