- During in-person session #2 (two weeks after in-person session #1), we will administer pre-LIFUP behavioral and motor testing, MRI, either LIFUP or sham stimulation (whichever was not received during the first session), and post-LIFUP motor testing.
- 48-72 hours after each in-person session, behavioral testing will be administered, as well as motor testing that can be conducted remotely.
- 4 and 7 days after each in-person session, a brief follow-up call will be conducted.
- Participants will be wearing the PKG device round-the-clock from one week prior to the first in-person session until one week after the second in-person session.
- The independent variable is the type of LIFUP modulation we will perform: active stimulation vs. sham stimulation.
- The dependent variables are: resting-state functional connectivity, perfusion, severity of motor symptoms, severity of psychological symptoms, and performance on the probabilistic learning task.

Detailed Design

Pre-screen: when we are put in contact with a potential participant, we will ask them to undergo a brief screening over the phone. The purpose of this session is exclusively to determine eligibility with respect to the following inclusion and exclusion criteria:

- **Inclusion Criteria:** (i) diagnosis of PD, (ii) age 18-85, (iii) fluent in English, (iv) hearing and vision normal or corrected-to-normal, and (v) willing and able to provide informed consent
- **Exclusion Criteria:** (i) mobility issues requiring use of a wheelchair or walker, (ii) significant cognitive impairment, (iii) history of neurological disorder other than Parkinson's, (iv) history of psychiatric disorders other than sleep disorders, anxiety disorders, and major depressive disorder, (v) pre-PD history of sleep disorders, anxiety disorders, and/or major depressive disorder, (vi) contraindication to MRI, (vii) medication changes within past 6 weeks or planned changes in next 6 weeks, (viii) pregnant or planning to become pregnant, (ix) history of medical event(s) likely to result in neurological abnormalities, (x) uncontrolled diabetes or hypertension, (xi) diagnosis of severe lung, liver, heart, or kidney disease, (xii) history of alcohol or substance abuse (other than nicotine or caffeine)

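### No active-versus-sham contrast is stated for the fMRI analyses made during stimulation, although fMRI is collected during both active and sham sonication

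*Combined protocol and SAP*

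**What the plan says.** PROCEDURES, Stimulation-related fMRI, describes three analyses:

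- a block-design model that will "compare the blood oxygenation level dependent (BOLD) signal during LIFUP stimulation blocks to the BOLD signal during no-stimulation blocks";
- a seed-based connectivity analysis that will "compare between stimulation (on-off) conditions using psychophysiological interaction modeling (PPI");
- a third analysis: "We will also use dynamic connectivity to evaluate changes in connectivity across the course of the LIFUP stimulation paradigm".

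The paragraph does not mention sham.

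APPROACH, fMRI Validated LIFUP stimulation, sets out a two-period crossover: "Participants will receive active sonication at one visit and sham sonication at the other, the order of which will be randomized and counterbalanced across participants". Its schedule is "20 ultrasound sonifications in a 30 s ON, 30 s OFF fashion". On the sham it says "For sham sonication, the gel pad will block close to all of the ultrasound energy from the transducer", and on acquisition "Resting state fMRI (rs-fMRI) will be collected simultaneously with LIFUP (or sham) sonication".

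STUDY DESIGN, Design Overview, says "The independent variable is the type of LIFUP modulation we will perform: active stimulation vs. sham stimulation". It attaches no model or contrast to this. Its list of dependent variables includes resting-state connectivity but not the block BOLD response.

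Among the imaging analyses, an active-versus-sham comparison is written out only for perfusion (PROCEDURES, Perfusion). APPROACH, Analysis and Publications, defers group-level analysis until 30 participants have been scanned and names no group-level contrast for BOLD or PPI.

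**The concern.** An ON-OFF contrast within one run shows that something changes when the blocks change. It does not show that ultrasound reaching the brain is the cause. Sound, vibration, interference in the image, or simply noticing that a block has begun would follow the same timing. The documents neither report nor rule out such responses.

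The sham pad acts downstream of the transducer, so the natural reading is that the transducer also runs in sham. The sham run would then carry the same switching without most of the ultrasound. It is the control that could separate the two explanations, and it is already being acquired.

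Dynamic connectivity has the same gap in another form: change over a run may come from time in the scanner as well as from stimulation.

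At stake is the reading of the during-stimulation part of Aim 3, and of any BOLD map offered as evidence that the target was engaged.

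**Working it through.** **1. What each contrast estimates.** Let τ be the effect of ultrasound on a participant's ON-OFF response, and let g_A and g_S be the mean non-specific responses under the active and sham pads. Taking the ultrasound that leaks through the sham pad as negligible:

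- active ON-OFF estimates τ + g_A;
- sham ON-OFF estimates g_S;
- active minus sham estimates τ + (g_A − g_S), which equals τ only if g_A = g_S.

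The same algebra applies to the PPI term.

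**2. Whether other parts of the plan remove g_A.**

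- The high-pass filter is set at 0.01 Hz. One ON/OFF cycle lasts 30 + 30 = 60 s, so its frequency is 1/60 = 0.0167 Hz and it is retained.
- The listed motion corrections are not aimed at a genuine sensory response locked to the blocks.
- Randomised order and pads of identical appearance protect comparisons between visits, not a contrast inside one run.

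**3. Size, as illustration.** There is no figure in the plan to reproduce: 30 participants is given without alpha, power, effect size or SD. Assume one test on participant-level ON-OFF estimates, n = 30, τ = 0 and g_A = d SDs of that estimate. The test statistic is noncentral t with 29 degrees of freedom and noncentrality d√30 (for d = 0.5, 0.5 × 5.477 = 2.74). Two-sided rejection rates are:

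| d (assumed) | alpha 0.05 | alpha 0.001 |
|---|---|---|
| 0 | 5.0% | 0.1% |
| 0.2 | 18.5% | 1.1% |
| 0.3 | 35.5% | 3.6% |
| 0.5 | 75.4% | 21.1% |
| 0.8 | 98.8% | 75.2% |

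Runs may be lost, for instance through the 0.5 mm mean-displacement exclusion. With n = 24 the alpha 0.05 column becomes 15.6%, 29.1%, 65.0% and 96.3% for d = 0.2 to 0.8.

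**4. The paired contrast under the same assumptions.** With g_A = g_S = 0.5 SD, 40,000 simulated trials at each between-visit correlation ρ (0, 0.3, 0.5, 0.7) rejected in 4.9% to 5.0% at alpha 0.05. No visit term was included. This follows from the assumed equality and is not evidence about this trial. If the two pads differ so that g_A − g_S = 0.2 SD, then at ρ = 0.5 the paired test is in the d = 0.2 row and rejects in 18.5%.

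**5. Precision.** With equal variances, the SD of the paired contrast relative to ON-OFF alone is √(2(1 − ρ)):

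| ρ | 0 | 0.2 | 0.5 | 0.8 |
|---|---|---|---|---|
| SD ratio | 1.41 | 1.26 | 1.00 | 0.63 |

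In SDs of a single-visit ON-OFF estimate, the effect detectable with 80% power at n = 30 and alpha 0.05 is 0.53 for ON-OFF alone. For the paired contrast it is 0.75, 0.63, 0.53 and 0.41 at ρ = 0, 0.3, 0.5 and 0.7.

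**The case against.** The strongest reply is that the paragraph describes within-run models and was never meant to fix the group-level contrast. Design Overview makes active versus sham the independent variable and lists resting-state connectivity as an outcome. It also treats sham as one type of LIFUP modulation, so the stimulation paradigms in this paragraph can be read as covering both runs. This shows intent, and it stands that far. It still supplies no test for BOLD, PPI or dynamic connectivity, and the block BOLD response is not among the listed outcomes.

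A reader might infer more: that the plan decides these questions on ON-OFF alone, leaves the sham run unused, and would report any response to the transducer as a LIFUP effect. The documents do not support this. The paragraph contains no decision rule or reporting rule, and no active-only group test is specified. What can be said is that no active-versus-sham contrast is stated.

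Three further objections stand as limits:

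- That the transducer is driven identically in sham is inferred from the pad blocking its energy.
- The sham pad lies against the scalp and might alter conducted sound or vibration, so equal non-specific responses cannot be taken for granted.
- The percentages describe one scalar test, whereas the PPI is whole-brain with no stated threshold. They change greatly between alpha 0.05 and 0.001.

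**Conclusion.** The gap is real. For three stimulation-period analyses the plan states only within-run contrasts, in a crossover that collects fMRI under both conditions and writes out the controlled comparison for perfusion. If the transducer is driven on the same schedule in sham, ON-OFF alone cannot attribute a response to ultrasound.

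How much this matters depends on a non-specific response whose size the documents do not give. Over an assumed 0.2 to 0.8 SD, the false-positive rate runs from 18.5% to 98.8% at alpha 0.05 and from 1.1% to 75.2% at alpha 0.001. At zero there is no inflation. These figures are illustrative, and they do not cover dynamic connectivity.

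The paired contrast removes non-specific responses only to the extent that they are equal under the two pads. The point should be settled before group-level analysis begins. It does not show that the sham data would be ignored or that a false claim would be made.

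**What to change.** In Stimulation-related fMRI:

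- Fit the same block and PPI models to the sham run, using its own ON/OFF timing.
- Make the paired difference, active ON-OFF minus sham ON-OFF, with a visit term, the group-level contrast on which a LIFUP effect is concluded.
- Apply the matching active-minus-sham difference to dynamic connectivity.
- Report within-visit maps as descriptive.

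In the section on LIFUP stimulation, state how the transducer is operated in sham and, if this is so, that it is driven identically. If it were silent in sham, the paired contrast would not remove responses to the transducer running. State also that the contrast relies on non-specific responses being equal under the two pads.

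The cost is wording and additional model fits and second-level contrasts, with no new scans or participants. Precision is lost when the between-visit correlation is below 0.5, up to an SD 1.41 times as large at zero correlation, and gained above 0.5. Participants without usable runs at both visits contribute less.

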The only data that will be retained about this screen is whether the participant is currently eligible, ineligible, or eligible at some future date, as well as their necessary contact information and any information necessary to verify MRI safety. No other record will be kept of the contents of the potential participant's answers.

Remote Session 1 [90 minutes]

The aim of this session is to (a) complete informed consent procedures, (b) evaluate cognitive status via the TICS-M (c) complete MRI safety screening procedures, (d) obtain participant demographic and medication information, (e) have caretaker complete part 1 of the TETRAS, and (f) schedule all other sessions

Remote PKG Setup Session [approx. 10 minutes]

The aim of this session is to (a) obtain a recording of the participant putting on the PKG device to ensure correct setup and (b) familiarize the participant with the usage of the device. Participant faces and voices will be removed from recordings before they are transferred from UCLA-owned devices to the UCLAHealth Box server. The PKG device will be worn from one week prior to the first in-person session to one week after the second in-person session. To collect continuous tremor data, the PKG device is to be worn round-the-clock, except for when participant is swimming, showering, syncing the device weekly, or in a LIFUP/MRI session.

In-Person Session 1 [approx. 4.5 hours]

This session will take place one week after the PKG setup session. The aim of this session is to (a) complete pre-LIFUP motor assessments (UPDRS, TETRAS, 1-minute forearm recording, grip strength and grooved pegboard tasks), (b) complete pre-LIFUP psychological assessments (SSS, STAI, RBDSQ, QUIP-RS, BDI), (c) perform neuronavigation-guided LIFUP or sham stimulation during rsfMRI, (d) collect information on any perceived changes immediately post-LIFUP, (e) collect pre-LIFUP high res T1w, PCASL, and rsfMRI scans and post-LIFUP PCASL and rsfMRI scans, (f) complete post-LIFUP motor assessments (UPDRS part 3, TETRAS part 2, grip strength and grooved pegboard tasks), and (g) complete post-LIFUP psychological assessments (SSS, PCQ).

Post-LIFUP Remote Session 1 [60 minutes]

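### No planned contrast compares the sonication run with the pre-stimulation scan, so a sustained connectivity shift that starts early would be missed by every stated during-run analysis

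*Combined protocol and SAP*

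**What the plan says.** Aim 3 reads "3: Measure BGTC network rs-FC before, during, and after LIFUP stimulation". The section on fMRI-validated LIFUP stimulation sets the timing as "20 ultrasound sonifications in a 30 s ON, 30 s OFF fashion" and has resting-state fMRI running throughout, under active and sham sonication alike.

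The Stimulation-related fMRI section plans three analyses of that run:

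- a block model comparing BOLD signal in stimulation blocks "to the BOLD signal during no-stimulation blocks";
- a seed-based connectivity analysis that will "compare between stimulation (on-off) conditions using psychophysiological interaction modeling";
- a third analysis: "We will also use dynamic connectivity to evaluate changes in connectivity across the course of the LIFUP stimulation paradigm".

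The RS-fMRI section covers comparison across scans. It states "We will compare rs-FC before and after stimulation", and then "Dual-regression analysis will then compare resting state networks between baseline and post-LIFUP". The sonication run is not named there.

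The data for a wider comparison will exist. In-Person Session 1 will "collect pre-LIFUP high res T1w, PCASL, and rsfMRI scans and post-LIFUP PCASL and rsfMRI scans", and In-Person Session 2 also collects PCASL and resting-state scans before and after stimulation.

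**The concern.** The reference for the block model and the PPI is the OFF block, which comes 30 s after its ON block began. That suits a response that switches on and off with the ultrasound. It does not suit one that outlasts it, and much of the plan looks for effects that do: PCASL and resting-state scans after stimulation, motor tests after the scan, and persistence over two weeks.

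A lasting change in coupling is present in ON and OFF blocks alike. In a PPI model it loads on the main effect of the seed, not on the interaction. Subtracting the sham ON-OFF estimate does not bring it back, because it has already cancelled within the active run.

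Dynamic connectivity looks for change within the run. If the shift occurs near the start and then holds, there is little change left to find. The analysis that could use a true pre-stimulation reference, the dual regression, leaves the sonication run out. At stake is the during part of one of the four main aims: for one plausible kind of effect, no stated analysis would show it while stimulation is in progress.

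**Working it through.** The plan gives no power, effect-size or time-course figure here, so there is nothing to reproduce. The check asks how much of an effect each contrast would see.

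**Inputs from the plan.** 20 cycles of 30 s ON and 30 s OFF, so 20 × 60 s = 1,200 s = 20 minutes.

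**Assumptions.** The time constant τ is not in the documents and is varied. The delay to the post scan is not given either and is taken as 5 minutes. The pre-stimulation level is 0 and the full effect is 1. Haemodynamic lag is ignored. The plan does not define a summary for dynamic connectivity, so the mean of the last quarter of the run minus the mean of the first quarter serves as a simple proxy.

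**Model A, gradual build-up and decay.** dx/dt = (s − x)/τ with x(0) = 0, where s = 1 in ON and 0 in OFF, computed numerically over the 20 cycles. At periodic steady state ON − OFF = 1 − tanh(u)/u with u = 30/(2τ). For τ = 300 s, u = 0.05 and this is 0.001. Over the actual run it comes to −0.01, because each OFF block follows its ON block while the effect is still climbing.

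**Model B, immediate onset with decay in OFF.** The effect is 1 in ON and exp(−v/τ) at v seconds into OFF. The OFF mean is r = (τ/30)(1 − exp(−30/τ)). Then ON − OFF = 1 − r, and during − pre = (1 + r)/2. For τ = 300 s, r = 10 × (1 − 0.9048) = 0.952, so ON − OFF = 0.048 and during − pre = 0.976.

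**Remaining 5 minutes after sonication**, as a share of the level at the end: exp(−300/τ).

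| τ (s) | ON−OFF, A | ON−OFF, B | During−pre, A | During−pre, B | Last−first quarter, A | Last−first quarter, B | Left at 5 min |
|---|---|---|---|---|---|---|---|
| 10 | 0.39 | 0.68 | 0.50 | 0.66 | 0.002 | 0 | 0.000 |
| 60 | 0.01 | 0.21 | 0.48 | 0.89 | 0.075 | 0 | 0.007 |
| 300 | −0.01 | 0.05 | 0.38 | 0.98 | 0.285 | 0 | 0.368 |
| 600 | −0.01 | 0.02 | 0.29 | 0.99 | 0.298 | 0 | 0.607 |
| 1200 | −0.01 | 0.01 | 0.19 | 0.99 | 0.231 | 0 | 0.779 |

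**Reading the table.**

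1. Effects that ON-OFF sees well (τ = 10 s) have gone by a post scan 5 minutes later. Effects of which at least 37% remains by then (τ of 300 s or more) leave at most about 5% in ON-OFF, under either shape.
2. For those lasting effects, within-run change sees 0.23 to 0.30 if the effect builds gradually, and nothing if it plateaus early.
3. During-minus-pre sees 0.19 to 0.38 under gradual build-up and 0.98 to 0.99 under an early plateau.

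The gap is therefore the early plateau. Each stated analysis of the sonication run is blind or nearly blind to it, while a contrast with the pre scan would recover almost all of it.

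**The case against.** The best defence is that the plan divides the work sensibly. Block and PPI contrasts are meant to measure rapid, reversible responses. If a rapid and a sustained response coexist, the sustained part drops out as a constant and ON-OFF still estimates the rapid part. Sustained change is assigned to the baseline-versus-post dual regression and to PCASL before and after. Under gradual build-up, the within-run proxy sees about as much as during-minus-pre: 0.285 against 0.383 at τ = 300 s, 0.298 against 0.289 at 600 s, and 0.231 against 0.188 at 1200 s. All of this stands, and it limits the point to a sustained shift that starts early.

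A reader might infer more than the documents support:

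- **That ON versus OFF is the only during-run test.** It is not. Dynamic connectivity is planned in the same section and can detect gradual build-up.
- **That a lasting effect goes untested.** The baseline-versus-post contrast tests it. What is missing is its measurement during stimulation.
- **That cancellation is always near total.** At τ = 60 s, ON-OFF keeps 1% under gradual build-up but 21% under immediate onset. At 300 s the figures are about 0 and 5%. A claim of well under 1% would hold for one curve shape only.
- **That a null ON-OFF result will be taken as failure to engage the target.** No section says so. Transducer position is verified on a T1 image. Functional MRI is mentioned for targeting, but ON-OFF is not named as the criterion.
- **That Aim 3 promises a before-versus-during test.** It says measure, and names no contrast. A comparison across the three stages is the natural reading, not the literal text.

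**Conclusion.** The point holds in limited form. The plan specifies no contrast between the pre-stimulation scan and the sonication run, and no active-versus-sham contrast of the sonication run, although Aim 3 names all three stages and both scans are collected under both conditions. A sustained shift that begins early would be missed by the block model, the PPI and, for lack of a pre-stimulation reference, dynamic connectivity. It could still appear in the baseline-versus-post contrast if it lasts.

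The size, at most about 5% of a lasting effect left in ON-OFF, rests on an assumed time constant of 300 s or more and on two simple curve shapes without haemodynamic lag. The documents give no time course, so the true loss is unknown. The direction does not depend on the exact figure: the longer the effect lasts, the less of it ON-OFF can show. This is a worthwhile, inexpensive improvement. It does not invalidate the planned analyses.

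**What to change.** In the RS-fMRI section, extend the dual regression to three levels: the pre-stimulation run, the whole sonication run (ON and OFF blocks together) and the post-stimulation run. Prespecify during-minus-pre, compared between active and sham within subject, as the test of the during part of Aim 3.

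In the Stimulation-related fMRI section, keep the block, PPI and dynamic connectivity analyses. Define the dynamic connectivity summary and its reference. Add a sentence saying that the ON-OFF contrasts address rapidly reversible responses, so a null ON-OFF result does not rule out a sustained effect.

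The cost is wording plus analysis of scans already planned, with no added visits or scanning. There are three downsides. It adds one more voxel-wise contrast in a study of 30 participants. Run lengths may differ, so volumes may need to be matched across runs. Pooling ON and OFF blocks mixes rapid with sustained responses, so the during-minus-pre result should be read alongside the ON-OFF result.

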Perfusion. PCASL is an arterial spin labeling technique that measures cerebral blood flow. It produces a perfusion image with voxel values representing local perfusion rates. Within FSL we will perform a voxel-wise repeated measures analysis between the pre-LIFUP and post-LIFUP PCASL scans. By examining the differences between these two scans, we can determine the effects that LIFUP has on perfusion in the target region and other connected regions. We will also perform a repeated measures analysis of perfusion between conditions (LIFUP vs. sham). By examining subjects receiving sham on visit 2, we can compare pre-sham resting state fMRI and PCASL to the pre-LIFUP values at visit one, to determine the persistence of blood flow effects over a 2-week interval. This will suggest how frequently LIFUP would need to be administered during a more comprehensive clinical trial.

Motor Assessment. Subjects will undergo a motor evaluation with assessments of motor symptoms such as a grooved pegboard task, a 15-second recording of forearm and hand tremor, and dynamometer grip strength measurements. They will also complete The Essential Tremor Rating Assessment Scale (TETRAS) and the Unified Parkinson's Disease Rating Scale (UPDRS). The motor testing portion of the UPDRS will be video-recorded for research staff to review after the session in order to maximize rating accuracy. Any recordings containing participants faces will be exclusively stored locally on UCLA-owned devices kept in a locked room; any video transferred off these devices will first be edited to remove faces and any other identifying information. The original footage will be deleted once this editing is complete. Participants will complete all of these assessments both before and after the MRI/LIFUP portion of each session. We will also ask the participant's partner or caregiver to complete part 1 of the TETRAS during the first virtual session. In addition to the measurements taken during the in-person and virtual sessions, we will ask participants to wear a watch-style device called the Personal KinetiGraph (PKG) starting one week prior to their first in-person session and ending one week after their second in-person session. This device provides round-the-clock monitoring of tremor activity and sleep quality. Additionally, immediately after administering LIFUP or sham stimulation, we will be asking participants open-ended questions about any perceived changes.

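### The written test of the LIFUP effect on resting-state connectivity is pre versus post with no sham contrast, although sham scans are scheduled for every participant; dynamic connectivity has the same gap

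*Combined protocol and SAP*

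**What the plan says.** - **RS-fMRI (PROCEDURES).** The section opens with a before-versus-after comparison. Dual regression will then "compare resting state networks between baseline and post-LIFUP to determine the effect of LIFUP on resting state functional connectivity". On covariates: "Age, sex and education will be included as additional regressors". No condition, visit or order term is named.
- **Stimulation-related fMRI (PROCEDURES).** "We will also use dynamic connectivity to evaluate changes in connectivity across the course of the LIFUP stimulation paradigm". No sham comparison is named.
- **Perfusion (PROCEDURES).** The pre/post contrast is given the same causal reading ("we can determine the effects that LIFUP has on perfusion in the target region and other connected regions"), but a second analysis follows: "We will also perform a repeated measures analysis of perfusion between conditions (LIFUP vs. sham". The section's one use of sham-visit rs-fMRI compares the pre-sham scan at visit 2 with the pre-LIFUP scan at visit 1, to study persistence.
- **fMRI Validated LIFUP stimulation (APPROACH).** "Participants will receive active sonication at one visit and sham sonication at the other", in randomized, counterbalanced order. rs-fMRI is acquired during both kinds of sonication. In-Person Sessions 1 and 2 each schedule rs-fMRI before and after it.
- **Design Overview.** Active versus sham is named as the independent variable, and rs-FC is among the dependent variables.

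**The concern.** A pre/post comparison within the active session mixes the effect of LIFUP with everything else that changes between the two scans. The MRI Data Acquisition paragraph says: "Total time in the scanner will be approximately 75 minutes each session". Motion is dealt with in preprocessing; drowsiness and time in the scanner are not. The sleepiness scale is collected before and after each scan session, but the Psychological Assessment section ties it to assessment results, not to imaging. Age, sex and education do not change between the two scans, so as covariates they cannot remove an average shift.

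The label post-LIFUP adds to the difficulty, because the session descriptions use it as a time label at both visits. If it means active visits only, the post-sham rs-fMRI has no stated group analysis. If it covers both visits without a condition term, sham is pooled with active. Only a reading with an explicit comparison by condition isolates LIFUP, and none is written.

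Aim 3 (rs-FC before, during and after LIFUP) is at stake, and with it the part of Aim 4 that relates motor change to rs-FC change. Under the written rule, a positive rs-FC result could not be attributed to LIFUP.

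**Working it through.** The plan gives no figure to reproduce: the sample of 30 comes without alpha, power, effect size or SD. What follows is an illustration.

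**Inputs from the documents.** n=30; one active and one sham visit each; 20 cycles of 30 s ON and 30 s OFF, so a 1,200 s run; a 0.01 Hz high-pass filter; and the motion rule "Subjects with greater than 0.5mm mean framewise displacement will be excluded from analyses".

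**Assumptions.** One summary outcome, no LIFUP effect, no carryover, mean within-session drift d in SD units of one session's change score, and correlation ρ between the two sessions' change scores. These are single-test rates, not map-level error rates.

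**1. Active-only pre/post test.** Noncentral t with df = n−1 and noncentrality d√n. For d=0.2 and n=30 the noncentrality is 0.2 × 5.477 = 1.095.

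| Drift d | n=30, α=0.05 | n=30, three centred covariates (df 26) | n=24 (assumed exclusions) | n=30, α=0.001 |
|---|---|---|---|---|
| 0.1 | 8.3% | – | – | 0.3% |
| 0.2 | 18.5% | 18.4% | 15.6% | 1.1% |
| 0.3 | 35.5% | 35.3% | 29.1% | 3.6% |
| 0.5 | 75.4% | 75.1% | 65.0% | 21.1% |

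The covariates leave the rates almost unchanged.

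**2. Both sessions pooled, no condition term.** The standardized drift becomes d/√((1+ρ)/2). For d = 0.2 / 0.3 / 0.5 the rates are 23% / 45% / 86% at ρ=0.5 and 32% / 61% / 96% at ρ=0.

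**3. Active minus sham change.** With equal drift at both visits the mean difference is zero. In 40,000 simulations per case the test rejected 4.8% to 5.2% of the time at the 5% level, and 0.07% to 0.11% at the 0.001 level. If drift differs between the active and sham sessions by x, the standardized bias is x/√(2(1−ρ)):
- x=0.1: 6.6% (ρ=0) to 8.3% (ρ=0.5)
- x=0.2: 11.6% (ρ=0) to 18.5% (ρ=0.5), and 27.7% at ρ=0.7

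**4. Dynamic connectivity.** Suppose coupling rises linearly from 0.3 to 0.5 over the run. The true difference between the first and last 5 minutes is 0.475 − 0.325 = 0.150. In simulation 97% to 101% of it survived a 0.01 Hz high-pass. This shows only that filtering does not remove such a rise, not that one occurs.

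**5. Why block BOLD and PPI are not part of the main point.** With ON first, mean ON time and mean OFF time differ by 30 s, so a linear rise in coupling enters the PPI ON−OFF term at 30/1,200 = 2.5% of its size. With a 6 s lag it is 18/1,200 = 1.5%. Simulation gave 1.6% to 2.4%. For block BOLD, filtering and the alternation largely cancel slow drift.

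**The case against.** The strongest reply is that the design already answers the question. The Design Overview makes active versus sham the independent variable and lists rs-FC first among the dependent variables, order is randomized, and sham rs-fMRI is collected. Nothing says the pre/post comparison is the only rs-FC test, and nothing states a pooled analysis. This is then a gap in the analysis text, not in the design. That stands, and the conclusion is conditional for that reason. But the Design Overview supplies no model, and the RS-fMRI section is the only place that says how the rs-FC effect will be determined. The Perfusion section shows that the plan writes a sham analysis out where it has one.

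Second, the size rests on chosen drifts. That is also fair: at 0.05 SD the rate is only 5.8%. The figures show how the error grows with drift, not how large it is here.

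Third, the dynamic connectivity sentence makes no explicit causal claim, and its term for the stimulation run could cover both conditions. This part is weaker than the dual-regression part, but change across the run is still confounded with time in the scanner unless sham is compared.

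Fourth, sham subtraction fails when drift differs between the sessions, as step 3 shows. It is a better control, not a perfect one.

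**Conclusion.** The concern holds and should be fixed before the group analysis. Followed as written, the rs-FC rule is an uncontrolled pre/post test in a trial that has a randomized sham control for every participant. If a sham comparison is intended, the written rule and the design disagree and must be reconciled.

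The size cannot be fixed from the documents. Under the stated assumptions the single-test false-positive rate at 5% goes from 8.3% at a drift of 0.1 SD to 75.4% at 0.5 SD, against about 5% for the sham-subtracted contrast with equal drift. The conclusion covers rs-FC and dynamic connectivity. For block BOLD and PPI the sham contrast should simply be named: slow drift largely cancels there, and the documents identify no ON-locked effect other than the ultrasound itself.

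**What to change.** **Change.**
- State the tested rs-FC contrast as (post − pre) active minus (post − pre) sham, computed per participant on the dual-regression maps.
- Include visit as a regressor on the session change scores. With one difference map per participant, this is an order regressor coded +1/−1 and not de-meaned. Age, sex and education may stay as centred covariates.
- Use the corresponding active-minus-sham contrast for dynamic connectivity.
- Keep the within-active contrasts as descriptive.
- State that sham subtraction removes only what the sham session reproduces, and that it assumes no carryover that changes during the second session.
- Minor: for block BOLD and PPI, name (ON − OFF) active minus (ON − OFF) sham.

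**Cost.** Wording only, since the scans are already scheduled at both visits. The price is precision. The detectable effect at 80% power is multiplied by √(2(1−ρ)):

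| n | Pre/post alone | ρ=0 | ρ=0.25 | ρ=0.5 |
|---|---|---|---|---|
| 30 | 0.53 SD | 0.75 | 0.65 | 0.53 |
| 24 | 0.60 SD | 0.84 | 0.73 | 0.60 |

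The order term matters only if order becomes unbalanced, for example through motion exclusions. With an assumed 18/12 split, leaving it out or de-meaning it biases the contrast by (18−12)/30 = 0.2 times the period effect. Coded +1/−1, the bias is 0 and the standard error rises by a factor of √(1/(1−0.2²)) = 1.021, about 2%.
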